#### *12.3 Termination Procedures:*

This study may be temporarily suspended or prematurely terminated if there is sufficient reasonable cause. Written notification, documenting the reason for study suspension or termination, will be provided by the suspending or terminating party. If the study is prematurely terminated or suspended, the PI will promptly inform the IRB and will provide the reason(s) for the termination or suspension. The study team will notify the participants of the study termination.

Circumstances that may warrant termination or suspension include, but are not limited to:

- Determination of unexpected, significant, or unacceptable risk to participants
- Insufficient compliance to protocol requirements
- Data that are not sufficiently complete and/or evaluable

The study may resume once concerns about risks, protocol compliance, and/or data quality procedures are addressed and satisfy the IRB. Data collected for the study prior to the study termination will be handled in the following manner:

- If the study is terminated due to safety reasons, the data related to adverse events will be evaluated.
- If the study is terminated for any other reason, the regulatory and/or institutional document/data retention policies will apply.

## 13.0 Risks to Participants

### *13.1 Foreseeable Risks:*

#### *Immediate risks*

In controlled settings, psilocybin has a robustly established physical and psychological safety profile (Brown et al., 2017; Hasler et al., 2004; Johnson et al., 2008; Johnson and Griffiths, 2017). Psilocybin has been generally well-tolerated by subjects in experimental studies (Dos Santos et al., 2018), both in psychiatric patients (Carhart-Harris et al., 2017a, 2018; Griffiths et al., 2016; Grob et al., 2011; Ross et al., 2016) and in healthy volunteers (Barrett et al., 2018; Bravermanová et al., 2018; Carhart-Harris et al., 2012, 2013; Carter et al., 2005b; Gouzoulis-Mayfrank et al., 2002; Griffiths et al., 2011; Grimm et al., 2018; Hasler et al., 1997; Komter et al., 2015; Kraehenmann et al., 2015; Muthukumaraswamy et al., 2013; Nicholas et al., 2018; Quednow et al., 2012; Schartner et al., 2017; Turton et al., 2014; Umbricht et al., 2003; Vollenweider et al., 2007; Wittmann et al., 2007). The most common acute physiological effects include a moderate increase in pulse and blood pressure (Gouzoulis-Mayfrank et al., 1999; Griffiths et al., 2006; Johnson et al., 2008) and delayed, transient, dose-dependent headaches (Johnson et al., 2012).

## MEDICAL PROTOCOL (HRP-590)

### PROTOCOL TITLE: VISUAL SURROUND SUPPRESSION UNDER PSILOCYBIN

VERSION DATE: May 18, 2023

Risk of adverse psychological reactions collectively known as “bad trips” involve acute states of distress characterized by fear, panic, anxiety, disturbing feelings, and troubling thoughts (Johnson et al., 2008). Acute adverse psychological reactions can be minimized and mitigated in a controlled experimental session using a variety of well-established techniques that include careful screening of subjects, training of study personnel, holding the dosing session in a secure and comfortable physical environment, careful preparation of participants, and following established pre-session, session, and post-session protocols (Johnson et al., 2008). Should such states arise, and the participant is unable to work through this reaction and resolve on its own, we will have the nurse on site to assess any major physical complications that may arise, and if needed, pre-prescribed anti-anxiety or anti-psychotics will be administered after consultation about the case with the psychiatrist/clinician on call for the testing sessions. See Appendix D for a description of our crisis communication plan, should such a situation arise.

#### *Long-range risks*

Long-range risks, while very unlikely, include the possibility of triggering substance abuse, prolonged psychotic episodes, and lasting perceptual abnormalities (Johnson et al., 2008). Psilocybin has an extremely low abuse potential (Johnson et al., 2018a), does not induce cravings or withdrawal (Johnson et al., 2018a), and does not activate dopaminergic reward circuits critical to substance use disorders (Nichols, 2004). Psilocybin is thus generally regarded as safe to introduce to drug-naive subjects without risk of initiating abuse or habitual use (Johnson et al., 2008, 2018a). Lasting perceptual abnormalities can occur, especially in naive users, although their occurrence is rare and in most cases are very brief, not regarded as detrimental, and sometimes even regarded as pleasurable (Johnson et al., 2008). Hallucinogen persisting perception disorder (HPPD), a condition in which the acute perceptual effects of the drug persist for prolonged periods after the peak effects have subsided, is extremely rare, mostly associated with LSD use in combination with cannabis, and has not been reported as having occurred in participants in any modern studies with psychedelic drugs (Martinotti et al., 2018). Nonetheless, careful follow-up on perceptual abnormalities is recommended (Johnson et al., 2008). Prolonged psychotic reactions to psilocybin in clinical settings is extremely rare and has not occurred in participants in studies.

The relative safety of psilocybin extends beyond controlled clinical settings, as epidemiological data on illicit and ritual use shows that adverse reactions leading to hospitalization are relatively rare (Johnson et al., 2018b; Leonard et al., 2018). Since there is little to no risk of physical overdose (Brown et al., 2017; Johnson et al., 2008), most hospitalizations resulting from illicit use in the general population are due to emotional distress and unstable mental states (Leonard et al., 2018) and subside within 48 hours (Johnson et al., 2018b; Tylš et al., 2014).

In summary, psilocybin has a proven track record of safety when administered in controlled experimental settings that follow established protocols (Brown et al., 2017; Dos Santos et al., 2018; Hasler et al., 2004; Johnson et al., 2008; Johnson and Griffiths, 2017).

MEDICAL PROTOCOL (HRP-590)

PROTOCOL TITLE: VISUAL SURROUND SUPPRESSION UNDER PSILOCYBIN

VERSION DATE: May 18, 2023

Although not completely without risks, psilocybin does not impose unusual danger compared with other standard experimental treatments and interventions.

Niacin can elevate heart rate and cause the skin to become flushed, and some digestive complications at high doses, however we will not be giving participants a high enough dose to induce serious forms of these complications, but participants may experience them to some degree.

Risks of a Blood Draw: Events associated with venipunctures include discomfort, slight bruising, bruising, bleeding, lightheadedness, fainting, infection at the venipuncture site, nausea, anxiety and swelling at the venipuncture site. Blood draws will occur in a lab or clinical research unit and done by qualified medical professionals trained in phlebotomy.

EEG: Use of the electrodes during the electrophysiology session requires that subjects wear an electrode cap, which some people find uncomfortable. We will measure the subject's brain waves while they are at rest and when the subject is performing a number of tasks. Some minor skin irritation is possible in reaction to the electrode cap application; however, reddening of the skin from the pressure of the electrodes typically resolves within 24 hours. Subjects will be notified that scalp discomfort from the use of EEG equipment typically resolves within 24 hours. Study staff will provide support for the participants should they appear to become fatigued or frustrated during EEG. Subjects have the liberty of discontinuing this procedure at any point.

MRI Scanning: The MRI scanning device will be a 3.0 Tesla MRI scanner. This device has been evaluated by the FDA as having non-significant risk for persons more than one month of age and data already reviewed by the UMN IRB indicate that the 3.0 Tesla magnetic field does not pose a significant risk to human volunteers. All participants will be screened according to CMRR policies to minimize risks to participants. These are the specific risks related to MRI scanning:

1) Exposure to high magnetic field: The primary known hazard associated with exposure to a static high magnetic field is that the magnet exerts a strong force on ferromagnetic objects. Metallic objects that are entered the magnetic field can accelerate into the magnet potentially causing damage to the magnet or persons in the magnet room. In addition, implanted metallic objects can be displaced. MRI may not be appropriate in the presence of the following conditions: cardiac pacemaker; metal fragments in eye, skin, body; mechanical heart valve replacement; brain clips; venous umbrella; being a sheet-metal worker or welder; aneurysm surgery; intracranial bypass; renal, aortic clips; middle ear, eye, joint, or penile implants; joint replacements; hearing aid; neurostimulator; insulin pump; intra-uterine device (IUD); shunts/stents anywhere in the body; metal mesh/coil implants; metal plate/pin/screws/wires anywhere in the body, any other metal implants; permanent eyeliner or permanent artificial eyebrows. All participants will be thoroughly screened first over the phone before enrollment, then using the CMRR Safety Screening Form at the day of MR scanning. Participants that do not pass screening will not enter the CMRR where magnetic fields exist.

MEDICAL PROTOCOL (HRP-590)

PROTOCOL TITLE: VISUAL SURROUND SUPPRESSION UNDER PSILOCYBIN

VERSION DATE: May 18, 2023

- 2) Radiofrequency (RF): Radiofrequency pulses impart small amounts of energy into the participant. No ionizing radiation is used with MRI. Because the pulse sequences to be used fall within FDA guidelines and will not be operated outside of safe limits, we do not expect any hazard associated with power deposition. To prevent inadvertent application of significant energies which may result in heating, the scanning systems include monitoring with both a hardware and a software monitor. Participants will be instructed to report any heating sensation immediately, and that the scan could be stopped at any time if this occurs.
- 3) Peripheral nerve stimulation: Peripheral nerve stimulation from rapidly switching magnetic fields ( $dB/dt$ ) during the scanning procedure may occur. As a result, the participant may experience muscle twitching or tingling sensations lasting seconds to minutes. This is considered to occur seldomly. Participants are instructed that if twitches do occur, they should immediately inform the operator. This would be a short-lived side effect and reversible.
- 4) Acoustic noise: MR imaging creates acoustic noise because of pulsing currents through the gradient coils within the magnetic field. A repetitive tapping sound occurs as a result. Ear plugs are provided to the participant to prevent hearing damage and provide comfort
- 5) Claustrophobia: Some people undergoing this procedure become anxious and afraid when in closed spaces. Participants will be instructed that they can stop procedure at any time. The MRI technologist will be in communication with the participant during the scan and ask them how they are doing. In addition, participants will be given a squeeze ball to communicate an urgent need or concern. Participants are screened for claustrophobia before enrollment.
- 6) Anatomical abnormalities revealed: There is a possibility that the MRI scan would reveal unknown and unlooked for abnormalities such as a cyst, vascular abnormality or a tumor. The scan results will be routinely sent to a radiologist for review. If an abnormality is uncovered, the participants are informed of the results of the radiology review and are encouraged to follow up with their physician. We would provide participants physicians with a copy of the imaging data that we collect upon request.
- 7) Dizziness and nausea: Dizziness and nausea are rare though may occur if the participants head moves around while they are inside the magnet. If this occurs, this would be acute and reversible, and should resolve within a few minutes without intervention.

Clinical Assessment: Some of the question's participants will be asked may make them feel uncomfortable or upset. These pertain to psychiatric and medical history, behavioral and psychiatric symptomatology, and personal illegal drug use. Participants are informed that they do not have to answer any question that makes them feel uncomfortable. Coordinators interviewing the participants will remind them of this, as well as use empathy to gauge their discomfort. Staff will be sufficiently trained to handle these situations.

Privacy/Confidentiality Risks: Participation in research may involve a loss of privacy due to the nature of the questions that are asked during assessment visits and/or data collected. However, records will be handled as confidentially as possible. All participants will be assigned a unique study identifier that will be used to label all of their records only be accessible to specific study staff listed in the Delegation of Authority log. This link will connect the participant's

MEDICAL PROTOCOL (HRP-590)

PROTOCOL TITLE: VISUAL SURROUND SUPPRESSION UNDER PSILOCYBIN

VERSION DATE: May 18, 2023

identifying information, such as name, etc., to their assigned ID number. No identifying information will be used in any report or publications that may result from this study. All study records will be kept in a secure database. Paper records will be kept in locked cabinets in locked rooms.

Severity and relationship of adverse events: The Principal Investigator will be responsible for determining whether an adverse event (AE) is expected or unexpected. An AE will be considered unexpected if the nature, severity, or frequency of the event is not consistent with the risk information previously described for the study intervention.

The following guidelines will be used to describe severity.

- **Mild** – Events require minimal or no treatment and do not interfere with the participant's daily activities.
- **Moderate** – Events result in a low level of inconvenience or concern with the therapeutic measures. Moderate events may cause some interference with functioning.
- **Severe** – Events interrupt a participant's usual daily activity and may require systemic drug therapy or other treatment. Severe events are usually potentially life-threatening or incapacitating. Of note, the term "severe" does not necessarily equate to "serious".

The degree of certainty about causality will be graded using the categories below.

- **Related** – The AE is known to occur with the study intervention, there is a reasonable possibility that the study intervention caused the AE, or there is a temporal relationship between the study intervention and event. Reasonable possibility means that there is evidence to suggest a causal relationship between the study intervention and the AE.
- **Not Related** – There is not a reasonable possibility that the administration of the study intervention caused the event, there is no temporal relationship between the study intervention and event onset, or an alternate etiology has been established.

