**Figure 2. Schematic of surround suppression task (Schallmo and Murray, 2016)**

**Safety.** Participants will be instructed to immediately inform the study team if any serious concerns arise with their health during the study. The team will assess all adverse effects, including frequency, severity and relationship to study drug. For participants that experience adverse psychological effects, including, but not limited to suicidal ideation, likely or probably related to study drug, the participant will be instructed to speak with a mental health professional to assess their status, either by Drs. [name] or [name] (clinical Co-Investigators). Participants will be given a list of phone numbers to call in the event that they are experiencing distress, such as suicidal ideation, including the study investigator at the telephone number listed on the first page of the consent forms, and instructed that if they feel they are crisis, that they can call 911 and/or a Nationwide Suicide Hotline that is answered 24 hours a day with a skilled, trained counselor. One example is the National Suicide Prevention Lifeline at [name].

Participants will be pre-prescribed antipsychotics and antianxiety medications in case the participants or the study staff want to stop the psilocybin experience with these pharmacological interventions. These costs will be paid for by the study funding. Some antipsychotics, like Risperidone, are able to bind to 5HT2A to block the activation of this receptor in the presence of psilocybin, whereas anti-anxiety medications, such as benzodiazepines, will help calm down the participants should they become agitated or too

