## MEDICAL PROTOCOL (HRP-590)

PROTOCOL TITLE: VISUAL SURROUND SUPPRESSION UNDER PSILOCYBIN

VERSION DATE: May 18, 2023

first three participants during the pilot phase to assess any SAE/AE or other issues. We will determine together whether we can move forward with the full study design or if modifications need to be made. For the full study design, the team will meet regularly after each additional 10 participants are enrolled and complete the study protocol throughout the duration of the study. Research staff will prepare a report for the DSMB at least 1 week prior to each scheduled meeting. This report will include a protocol synopsis, study personnel, brief statement of purpose, projected timetable and schedule, study summary including a summary of protocol changes, enrollment/participant status, protocol deviations, and adverse event tables (incidence, severity, listing of serious adverse events, adverse events, and deaths) and anything else pertinent to the study, participant safety or DSMB oversight. Safety information will be collected on Case Report Forms, adverse event and protocol deviation logs, and on memos (memo-to-file) requiring additional explanation and PI signature.

The DSMB, along with FDA and UMN IRB, would determine the need to immediately suspend research based on any individual SAE/AE as well as collective AE/SAE parameters. The DSMB, in addition to the FDA and UMN IRB, will be notified of any SAE immediately. The DSMB will be notified in each annual report of the following: AE log (frequency, severity, corrective treatment, duration, relation to study drug, and serious or not serious of each event by participant ID), AE incidence and severity by body system, and listing SAE/deaths.

See Appendix (G) for the DSMB members and charter.

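### The Related and Not Related adverse-event grades overlap, so the relation-to-study-drug entry in the DSMB's log can depend on which clause the rater applies

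*Combined protocol and SAP*

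**What the plan says.** Section 13.1 (Foreseeable Risks, under severity and relationship of adverse events) introduces the grades with "The degree of certainty about causality will be graded using the categories below" and gives two.

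- **Related** has three alternatives. The first is "The AE is known to occur with the study intervention". The second and third are "there is a reasonable possibility that the study intervention caused the AE, or there is a temporal relationship between the study intervention and event". One clarifying sentence follows: "Reasonable possibility means that there is evidence to suggest a causal relationship between the study intervention and the AE".
- **Not Related** also has three alternatives. The first is that there is no reasonable possibility that giving the intervention caused the event. The other two are "there is no temporal relationship between the study intervention and event onset, or an alternate etiology has been established".

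Section 5.2 (Safety paragraph) says who rates: "The team will assess all adverse effects, including frequency, severity and relationship to study drug". The Principal Investigator is named in section 13.1 only for deciding whether an event is expected. The same Safety paragraph attaches an instruction to adverse psychological effects that are "likely or probably related to study drug", a phrase that matches neither grade.

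Section 18.2 says where the grade goes. The DSMB's annual report includes an "AE log (frequency, severity, corrective treatment, duration, relation to study drug, and serious or not serious of each event by participant ID".

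**The concern.** Two categories meant to divide all events should be exclusive and exhaustive. Here each is a list of alternatives joined by an or, and a single event can satisfy one alternative from each list. Two careful raters could then enter opposite grades for the same event, and both would be following the protocol.

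The schedule makes such events plausible. Under section 5.2, blood is drawn at each part of Visits 3 and 5, and the first MRI scan after each dosing session falls within 24 hours. Section 13.1 lists bruising, nausea and anxiety among the risks of venipuncture, and anxiety, dizziness and nausea among those of MRI. An event that a procedure causes on the day after dosing is close in time to the drug and has another cause.

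At stake is whether the relatedness entry that the DSMB reads means the same thing from one event to the next.

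**Working it through.** The plan gives no figure to reproduce, so the check is logical. Describe an event by four yes/no facts taken from the wording of section 13.1:

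- K: it is a known effect of the intervention
- R: there is a reasonable possibility that the intervention caused it
- T: there is a temporal relationship
- A: another cause has been established

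As written:

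- Related = K or R or T
- Not Related = (not R) or (not T) or A

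Four facts give 2 × 2 × 2 × 2 = 16 patterns. An event escapes Not Related only when R and T hold and A does not. K is then free, so 2 patterns are Related only. An event escapes Related only when K, R and T all fail. A is then free, so 2 patterns are Not Related only. The remaining 16 − 2 − 2 = 12 meet both definitions, and none meets neither.

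The needle-site bruise on the day after dosing has T = yes and A = yes. With those two fixed, K and R leave 4 patterns, and all 4 meet both definitions. The same conflict arises for a known effect of the drug with no temporal link to dosing (K = yes, T = no), which is Related by the first clause and Not Related by the second.

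Softer readings of Not Related were also tried:

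| Reading of Not Related | Both | Related only | Not Related only | Neither | Close in time with another cause |
|---|---|---|---|---|---|
| As written: (not R) or (not T) or A | 12 | 2 | 2 | 0 | both, 4 of 4 |
| ((not R) and (not T)) or A | 8 | 6 | 2 | 0 | both, 4 of 4 |
| (not R) and (not T) and A | 1 | 13 | 1 | 1 | Related only, 4 of 4 |

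Only the last reading resolves the bruise. It replaces every or with an and, against the text, and still leaves one pattern in both grades and one in neither. The clarifying sentence does not help, because it explains the reasonable-possibility clause and does not limit the timing clause.

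These are counts of logical patterns. Some combinations will be rare or absent in practice, so 12 of 16 is not an expected share of events.

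The outputs described in section 18.2 can be set against the grade as follows:

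- Relation-to-study-drug field in the AE log: depends on the grade.
- AE incidence and severity by body system: not described as split by relatedness.
- Listing of serious events and deaths: not filtered by relatedness.
- Immediate notification of serious events: covers all of them, whatever the grade.

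**The case against.** The best defence is that causality grading is a judgement, and that an experienced rater would let the more specific clause win. A bruise at a needle site would be called Not Related without hesitation. That is probably how many such events would be graded, but the protocol does not say so, and the timing clause says the opposite. For anxiety in the scanner on the day after dosing, it is less clear that another cause would count as established. That example is therefore weaker than the bruise.

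The defence is right about reach. Several stronger readings are tempting, and the documents do not support them.

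- A reader might infer that the DSMB's safety counts in general depend on the rater. Section 18.2 does not filter its tables, listings or serious-event notification by relatedness, and the log shows each event alongside its severity, treatment and duration.
- A reader might infer that a related-event rate, or a drug comparison of related events, would be distorted. Section 15 plans no such analysis, and section 18.2 states no suspension threshold based on relatedness.
- A reader might infer that the drug supplier receives unreliable causality data. Section 6.1 promises de-identified safety data and does not say that relatedness is included.
- A reader might size the problem from the follow-up schedule: 3 days × 2 sessions × 40 participants = 240. That counts visit days, not events. No event rates are given, and no window defines a temporal relationship, so it cannot be said that most procedure-related events fall in the overlap.

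The DSMB charter (Appendix G) was not among the supplied text, so a tie-break rule there cannot be excluded. It would still leave section 13.1 contradictory for the staff who grade events.

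**Conclusion.** The point holds within narrow limits. It concerns a stated rule that gives contradictory grades, not a missing detail. An event close to dosing with an established other cause is both Related and Not Related under section 13.1, and nothing supplied says which clause prevails. The consequence is confined to one field in the AE log and any count by relatedness drawn from it. No endpoint, planned analysis, incidence or severity table, serious-event listing or serious-event notification is affected as described.

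The number of events affected cannot be estimated from the documents. The conclusion assumes that the clauses are read as written, or under the softer reading in which another cause alone still suffices for Not Related, and that no precedence rule stands in material that was not supplied. It is worth correcting because the text is wrong as written and the correction is cheap.

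**What to change.** Rewrite the two grades in section 13.1 so that they are exclusive and exhaustive. Classify on one question: is there a reasonable possibility that the study intervention caused the event? Yes is Related and no is Not Related. Timing, known effects of the intervention and other causes become evidence for that answer, and none is sufficient alone. In the notation above, Related = R and Not Related = not R. The 16 patterns then split 8 and 8, with none in both and none in neither.

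Apply the rule to any events already logged. Reconcile the causality phrase in the Safety paragraph of section 5.2 with the grades in section 13.1, so that the two sections use the same terms. Recording separately whether an event is due to a study procedure would be a useful addition, but it is optional.

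The cost is a few lines of protocol and case report form wording, plus regrading of any events already logged. No new data are needed.
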